5.5.1.3.2. Time to Event Endpoints Based on Other Parameters

5.5.1.3.2.1. Time to JNJ-3989 Off-Treatment HDV Relapse

It is defined as the number of days between the date of EOT and the date of the first occurrence of JNJ-3989 off-treatment HDV relapse as defined in Section 5.5.1.1.4. The participants who withdrew during the FU phase before the end of the study and before achieving the event or without achieving it will be censored at the last available HDV RNA assessment during the FU phase.

5.5.1.4. Additional Efficacy Endpoints Relative to The Actual Duration of JNJ-3989 Treatment

This section intends to evaluate some selected efficacy endpoints over time conditional upon the same treatment duration with JNJ-3989 across the 2 arms based on Part 2 data. For example, DB

Week 24 for Arm 1 corresponds to Week 76 for Arm 2 (Week 52+24, See [Table 2](#)), as participants in Arm 2 start treatment with JNJ-3989 at Week 52 when they switch over to the active regimen. For each DB Week X for Arm 1 data, the corresponding Week 52+X for Arm 2 data will be considered, as described in [Table 5](#):

Table 5: Correspondence between timepoints for Arm 1 and Open Label timepoints for Arm 2

Analysis Time point for Arm 1 (label)	Matching Analysis OL Timepoint for Arm 2 (label)
Baseline	Week 52
Week 2	Week 54
Week 4	Week 56
Week 8	Week 60
Week 12	Week 64
Week 16	Week 68
Week 20	Week 72
Week 24	Week 76
Week 28	Week 80
Week 32	Week 84
Week 36	Week 88
Week 40	Week 92
Week 44	Week 96
Week 48	Week 100
Week 52	Week 104
Week 56	Week 108
Week 60	Week 112
Week 64	Week 116
Week 68	Week 120
Week 72	Week 124
Week 76	Week 128
Week 80	Week 132
Week 84	Week 136
Week 88	Week 140
Week 92	Week 144
Week 96	EOT (only for OL completers)

When applicable, the reference timepoint (RT) for those analyses will be baseline (DB Day 1) for Arm 1 and Week 52 for Arm 2.

The following endpoints will be presented for those time points during the open-label phase in Arm 2 that match the treatment duration in Arm 1 during the double-blind phase, because of the deferred active trial design, as per [Table 5](#).

The selected endpoints are:

- Proportion of participants with HDV RNA $\geq 2 \log_{10}$ IU/mL decline from RT or HDV RNA TND in combination with normal ALT
- Proportion of participants with HDV RNA $\geq 2 \log_{10}$ IU/mL decline from RT or HDV RNA $<$ LLOQ in combination with normal ALT

- Proportion of participants with HDV RNA $\geq 2 \log_{10}$ IU/mL decline from RT or HDV RNA TND
- Proportion of participants with HDV RNA TND
- Proportion of participants with HDV RNA <LLOQ
- Proportion of participants with normal ALT
- Proportion of participants with LSM reduction ≥ 2 kPa from RT
- Proportion of participants with HBsAg seroclearance i.e. with HBsAg < LLOQ, with HBsAg < 1 IU/mL and < 10 IU/mL
- Change from RT in HDV RNA
- Change from RT in ALT
- Change from RT in HBsAg
- Change from RT in LSM

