1.2. Trial Design

Prior Protocol Amendment #4 the study was planned to include 2 parts, Part 1 (approximately N=20) with proof of concept objectives and Part 2 (approximately N=145) with confirmatory objectives. As of Protocol Amendment #4, Part 2 sample size was reduced to 30 participants which triggered modifications of objectives of Part 2 from confirmatory to exploratory.

Part 2 of the study will only be initiated once the antiviral activity criteria in Part 1 have been met and after evaluation of the results of the first IA during the double-blind phase of Part 1. Cirrhotic participants will be excluded from participation in Part 2 of the study.

Each part includes 3 phases: a 4-week screening phase (may be extended up to a maximum of 6 weeks), 144-weeks study intervention phase (Arm 1) and 148-weeks study intervention phase (Arm 2), 48-week follow-up phase. The first 52 weeks of the intervention phase are double-blind followed by 96 weeks of open-label (OL) treatment.

In each part the participants will be randomized in a 4:1 ratio to Arms 1:2.

- Arm 1: 100 mg JNJ-3989 (subcutaneous [SC] injection every 4 weeks [Q4W]) + NA qd for 144 weeks;
- Arm 2: placebo for JNJ-3989 (SC injection Q4W) + NA qd for 52 weeks, followed by 100 mg JNJ-3989 (SC injection Q4W) + NA qd for 96 weeks (control deferred active treatment arm).

Randomization will be stratified by presence of compensated cirrhosis at screening (yes or no) (Part 1 only), HDV RNA testing laboratory location (China versus outside China) (all sites in China will utilize the laboratory testing in China and all sites in other countries will utilize the laboratory outside of China), and HBeAg status at screening (positive versus negative).

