Prior Protocol Amendment #4, if safety was confirmed and futility excluded in Part 1, the total number of participants in this study was planned to be approximately 165 participants (specifically with a target of approximately 20 participants in Part 1, and 145 participants [up to a maximum of 170 participants] in Part 2), aged ≥ 18 to 65 years of age, co-infected with HDV and HBV. An interim analysis (IA) during DB study intervention phase was planned to re-assess the sample size in Part 2 and potentially increase it to maintain the statistical power at minimum at 80%. The maximum total sample size allowed for Part 2 of this study was 170. A reduction in sample size was not allowed, hence the minimum sample size for Part 2 was the planned number of 145 participants (see Section 1.4). The confirmatory conclusions of the study would be based on data from Part 2 only (145 participants, or, if recommended by IDMC, up to 170 participants). As Per Protocol Amendment #4, the total sample size of the study is 52, with 22 participants in Part 1 and 30 participants in Part 2. Data from Part 1 and Part 2 will be reported both separately and together to contribute to the overall benefit/risk ratio assessment of the regimen.

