1.5. Randomization and Blinding

Randomization and Stratification

Randomization will be performed using a 4:1 ratio (Active regimen from the start Arm1 : Placebo/deferred treatment Arm 2), regardless of the study part, to minimize bias in the assignment of participants to intervention arms, to increase the likelihood that known and unknown participant attributes (eg, demographic and baseline characteristics) are evenly balanced across treatment arms, and to enhance the validity of statistical comparisons across intervention arms.

Randomization will be stratified by presence of compensated cirrhosis at screening (yes or no) (Part 1 only), HDV RNA testing laboratory location (China versus outside China), and HBeAg status at baseline (positive versus negative) in order to provide an evenly balanced representation across the 2 arms.

Blinding

Blinded treatment will be used to reduce potential bias during data collection and evaluation of clinical endpoints.

The investigators, participants and all site personnel will remain blinded to study intervention allocation until Week 52 (Part 1) and Week 48 (Part 2). After Week 52 (Part 1) and Week 48 (Part 2), it will be communicated to the investigators whether the participants were allocated to either the investigational arm (Arm 1) or the control arm (Arm 2) to allow the correct open-label and follow-up visits schedule to be followed (see Schedules of Activities). For each participant, all HDV RNA, HBsAg, HBeAg, HBcrAg, anti-HBs, and anti-HBe antibody testing individual results will be provided to the investigator and the sponsor for managing the participant's safety.

After Week 52 and up and until Week 144, study intervention will be administered in open-label fashion to all participants (except Part 2 participants allocated to Placebo+NA who had HBsAg >10,000 IU/mL at screening or baseline).

Prior to Part 1 IA1 (see Section 3.3.2.1.1), the Sponsor Committee will review unblinded aggregated interim data of HDV RNA, HBsAg, ALT, AST, total and direct bilirubin, HBV DNA and individual patient profiles for the values/changes from baseline over time for all participants in Part 1 including those randomized to the placebo+NA arm.

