2.2. Baseline

In general, the baseline assessment is defined as the last observed non-missing measurement before the date and time of the first administration of any of study treatments.

In case the first administration time is missing, the first observed measurement on DB Day 1 will be used as the baseline measurement. If no observed measurement on DB Day 1, the last observed measurement before DB Day 1 will be used as the baseline assessment.

An additional reference timepoint (RT) will be used for an additional analysis of selected efficacy endpoints for Part 2 relative to the actual duration of treatment with JNJ-3989 as motivated by the deferred treatment design. This is described in Section 5.5.1.4.

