5. EFFICACY

The primary analysis set will be the ITT analysis set (see definition in Section 2.3), unless specified otherwise. Efficacy assessments over time will be performed at the analysis time points defined in Section 2.1.3. However, the use of the mITT analysis set (instead of ITT) in the efficacy analyses will be determined based on the impact of the COVID-19 or similar pandemics and assessed prior to the database lock for the first IA during DB study intervention phase.

All efficacy data will be summarized by study Parts 1 and 2, as well as for the whole study data overall:

- For DB study intervention phase: by study intervention arm over time (when applicable), as well as by study part (1 and 2).
- For OL study intervention and Follow-up phases: by study intervention arm over time and by study part 1 and 2. Additional selected efficacy analyses will be conducted to compare the OL study intervention data from Week 52 to Week 148 in Arm 2 with data from the first 96 weeks of DB study intervention in Arm 1 (i.e same duration of exposure to JNJ-3989+NA in both arms). See Section 5.5.1.4 for more details.

Subgroup analyses will be conducted on Part 2 data alone as well as combined data (Part 1 and Part 2) to leverage the total sample size of the entire study. Subgroup analyses will be performed if their size is at least 10% of the total sample size. All analyses will be presented only in a descriptive fashion.

For OL intervention and FU study phases, all efficacy data will be presented only descriptively, and no formal testing will be performed.

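### The exposure-matched analysis of the deferred arm is limited to Part 2 (about 6 expected controls, fewer after the roll-over exclusion), against the SAP's by-part-and-overall rule; extending it to Part 1 is a cheap, minor improvement

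*SAP*

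**What the plan says.** Section 5.5.1.4 puts both arms on a clock that starts with the first JNJ-3989 dose. Table 5 pairs each Arm 1 visit with the Arm 2 visit 52 weeks later. Where an endpoint is a change or decline, it is measured from Day 1 in Arm 1 and from Week 52 in Arm 2. The section does this "conditional upon the same treatment duration with JNJ-3989 across the 2 arms based on Part 2 data". Section 2.2, which introduces the second reference timepoint, says it is "for an additional analysis of selected efficacy endpoints for Part 2 relative to the actual duration of treatment with JNJ-3989".

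The general rules are wider. Section 5 states: "All efficacy data will be summarized by study Parts 1 and 2, as well as for the whole study data overall". Section 5.5.2 says the same of secondary efficacy data, and Section 1.2 says the two parts will be reported apart and together. Section 5 also announces this very comparison inside a bullet on open-label and follow-up results by arm and by part, with no limit to Part 2.

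On numbers, Section 1.2 says "In each part the participants will be randomized in a 4:1 ratio to Arms 1:2" and "the total sample size of the study is 52, with 22 participants in Part 1 and 30 participants in Part 2". On the switch, Section 1.5 gives open-label JNJ-3989 after Week 52 to everyone, "except Part 2 participants allocated to Placebo+NA who had HBsAg >10,000 IU/mL at screening or baseline". Section 5.5.1.4 does not mention this exclusion. It describes Arm 2 participants as starting JNJ-3989 at Week 52, without exception.

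**The concern.** Three things come together.

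- **Scope.** The specific text (2.2, 5.5.1.4) and the general text (1.2, 5, 5.5.2) do not agree. Two programmers could produce different tables. If the specific text governs, as it normally would, Part 1 is left out.
- **Size.** Part 2 was planned at 145 participants and now has 30, so the deferred arm on which this display depends has become very small.
- **Selection.** Only in Part 2 is the switch conditional on HBsAg. Nothing in 5.5.1.4 applies the same condition to Arm 1, so the Part 2 columns set an Arm 1 not restricted on HBsAg against switchers who are. This is plausibly related to outcome. The rationale for Amendment 5 reports that ALT elevations in Part 2 were more frequent above 10,000 IU/mL, and normal ALT, change in ALT and change in HBsAg are among the listed endpoints.

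At stake is how much the deferred arm can show on the Week 52 clock. No primary or key secondary result depends on it.

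**Working it through.** **Inputs.** Allocation 4:1 in each part, and 22 and 30 participants (Section 1.2; Section 1.4 gives 20 for Part 1). Earlier Part 2 plan of 145 (Section 1.2). Roll-over exclusion in Part 2 only (Section 1.5). The SAP gives neither actual arm counts nor the number excluded from roll-over.

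**1. Check of the allocation against the SAP's own figure.** Section 3.3.3 counts 16 Arm 1 participants in a Part 1 of about 20: 20 × 4/5 = 16. The ratio reproduces it.

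**2. Expected Arm 2 sizes (N/5).**
- Part 2 as first planned: 145/5 = 29.
- Part 2 now: 30/5 = 6, with 24 in Arm 1.
- Part 1: 22/5 = 4.4 (20/5 = 4), so about 4, with about 18 in Arm 1.
- Both parts: about 10 and about 42.

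**3. Effect of the roll-over exclusion.** Let q be the share of Part 2 controls excluded. It is unknown, so a range of 10% to 60% is assumed; zero is also possible.
- Part 2 switchers = 6 × (1 − q): 5.4 at 10%, 2.4 at 60%.
- With about 4 from Part 1: 9.4 and 6.4.

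**4. Precision for one arm.** If none of n participants responds, the exact 95% upper limit is 1 − 0.025^(1/n):

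| n | 3 | 4 | 6 | 8 | 10 |
|---|---|---|---|---|---|
| upper limit | 71% | 60% | 46% | 37% | 31% |

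**5. Precision for the difference.** For illustration, assume 30% response in both arms. Half-width = 1.96 × √(0.21/n₂ + 0.21/n₁).
- Part 2 alone: 6 vs 24 gives 0.41; 4 vs 24 (two not switching, assumed) gives 0.49.
- Both parts: 10 vs 42 gives 0.32; 8 vs 42 gives 0.35.

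At 4 to 6 participants this normal approximation is rough. It shows direction and order of size only.

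**6. Can Part 1 supply the data?** Section 1.2 gives each part the same phases, arms and Week 52 switch. Tables 2 and 5 make no distinction by part, so the visit mapping carries over unchanged.

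**7. What is lost for Part 1?** Section 5.5.1.4 lists twelve endpoints. Four need no reference timepoint: HDV RNA not detected, HDV RNA below the quantification limit, normal ALT, and the HBsAg thresholds. For these, Part 1 lacks only the side-by-side alignment of Table 5. The other eight involve change or decline, and for them Part 1 also lacks the re-baselining at Week 52.

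**The case against.** Restricting to Part 2 can be defended. Part 1 admitted compensated cirrhosis and Part 2 does not (Section 1.2). The rationale for Amendment 4 says the HBsAg and HDV RNA inclusion criteria were also adapted for Part 2, and these are two of the markers analysed here. The primary and key secondary estimands are for non-cirrhotic participants and use Part 2 data, so 5.5.1.4 matches their population. The SAP gives no reason for the restriction, so calling it a leftover of the confirmatory design is inference. All this stands, and it is why a combined column must never appear without the separate parts.

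A reader might infer that Part 1's deferred-arm data, some 4 of 10 switchers or 4 of 8, are thrown away. The documents do not support that. Sections 5 and 5.5.2 already have open-label results summarised by arm and part, so only the alignment and re-baselining are missing.

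A reader might also infer that Part 1 has an intact control arm. That describes the plan only. The rationale for Amendment 3 reports ALT elevations in about half of the 22 participants and new discontinuation criteria, and nothing says how many Part 1 controls reached Week 52 and switched.

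Finally, open-label efficacy is descriptive under Section 5, and the display is imprecise with or without Part 1. That stands too and sets the severity.

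**Conclusion.** The point holds as a minor one. Sections 2.2 and 5.5.1.4 are narrower than the SAP's own reporting rule. They confine a descriptive display to a part with about 6 expected controls, of whom an unstated number do not switch, and they leave out about 4 Part 1 controls to whom the HBsAg exclusion does not apply. Adding Part 1 takes the deferred arm from about 6 to about 10 before the exclusion. That is a modest gain, and the result remains imprecise.

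It is tempting to conclude that pooling would cure the selection in Part 2. It would not: the combined column still holds the selected Part 2 switchers against Arm 1 participants above 10,000 IU/mL. Only the separate Part 1 column, or a Part 2 display matched on HBsAg, avoids that imbalance.

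The conclusion rests on expected counts from 4:1 allocation, on an assumed range for the excluded share, and on the Week 52 switch in Part 1 having gone broadly as planned.

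**What to change.** In Sections 2.2 and 5.5.1.4, replace the Part 2 restriction by 'by study part and for both parts combined'. Define the Week 52 reference timepoint for Arm 2 of both parts and show the by-part columns beside the combined one.

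For Part 2 and the combined column, state how many Arm 2 participants did not switch. Add a display in which Part 2 Arm 1 is limited to participants with HBsAg at or below 10,000 IU/mL at both screening and baseline, the mirror image of the roll-over rule. This needs its own flag: the HBsAg categories in Section 2.4.1 place exactly 10,000 in the upper group and use either baseline or screening, not both.

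The cost is a wording change and a few more descriptive tables, on a visit mapping that already exists. The downside is a combined column that mixes parts with different cirrhosis, HBsAg and HDV RNA eligibility, which the adjacent by-part columns keep visible.

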5.5.2. Analysis Methods

All secondary efficacy data will be summarized by study Parts 1 and 2, as well as for the whole study data overall.

All other secondary endpoints at Week 48 will be analyzed and summarized as described in Section 5. No adjustment for multiple endpoints will be made.

All secondary endpoints evaluated at all other time points different than Week 48 during the study will be summarized descriptively by intervention arm, by phase and time point. No imputation rule will be used in case of missing data and the analysis will be based on observed cases.

5.5.2.1. Binary Endpoints

The binary endpoints will be analyzed using the stratum-adjusted MH test similar to the primary efficacy endpoint with corresponding 95% CIs on the difference of proportions.

The number and proportion of participants achieving the endpoints defined in Section 5.5.1.1 will be summarized over time with associated 95% CI. Between-arm difference in proportions with 95% CI will also be provided for all timepoints.

Bar charts will be provided for proportions in each intervention arm.

Cumulative percentage of participants achieving any given decrease from baseline at Week 48 in selected virology markers (e.g. HBsAg, HBV DNA etc.) will be presented graphically.

Subsections below describe the additional analyses planned for only those specific other secondary binary endpoints that require further evaluations.

5.5.2.1.1. HDV RNA

In addition to the summaries described in Section 5.5.2.1, shift tables in HDV RNA categories from baseline will be provided.

In an additional summary, the proportions will be calculated based on the number of participants who have achieved HBsAg seroclearance at the FU weeks of interest after stopping JNJ-3989, regardless of continuing NA.

5.5.2.1.2. HBsAg Seroclearance

The proportion of participants who achieve HBsAg seroclearance will be summarized over time for all time points.

5.5.2.1.3. HBsAg Seroconversion.

For all participants achieving HBsAg seroconversion, descriptive statistics will be calculated for the level of anti-HBs antibodies at the timepoint when achieving the HBsAg seroconversion by intervention arm. In an additional summary, the level of anti-HBs antibodies will be summarized over time for the subset of the participants achieving HBsAg seroconversion at any time before or at that given timepoint by intervention arm.

Furthermore, the number and proportion of participants with appearance of anti-HBs antibodies and without HBsAg seroclearance will also be summarized.

5.5.2.1.4. HBV Flares

The incidence rate will be calculated and summarized for each type of on-treatment or off-treatment flares (virologic, biochemical and clinical) separately, as well as the overall incidence of participants experiencing at least one flare, regardless of type. Additionally, for each participant the total number of flares the participant experienced will be counted by type. Such counts will be used to summarize the distribution of the total number of flares by type and by intervention arm.

For on-treatment biochemical flares, the incidence of flares causing treatment discontinuation will be summarized. Further, for off-treatment flares, the count and percentage of participants who experienced a flare followed by NA re-treatment will be summarized by flare type. Similarly, the incidence of flares followed by the achievement of HBsAg seroclearance (at any time) will be summarized by flare type. Flares that are associated with signs of liver decompensation will be provided in a listing.

5.5.2.1.5. HBV DNA Cut-offs

The proportion of participants achieving HBV DNA cutoffs described in Section 5.5.1.1.10 will be summarized over time for all time points.

In an additional summary, the proportions will be calculated based on the number of participants who have achieved HBV DNA cutoffs at the FU weeks of interest after stopping all study interventions including NA.

5.5.2.2. Values and Change Over Time

Continuous variables will be summarized using descriptive statistics including the number of participants in the analysis, mean, standard deviation (SD), two-sided 95% CIs, median, and range. Descriptive statistics on actual values (original unit and \log_{10} transformed values, when appropriate) and changes from baseline (\log_{10} transformed values when appropriate) will be summarized over time. Mean (+/- SE) plots of the actual values and the change from baseline (\log_{10} transformed when appropriate) will be presented over time.

Spaghetti plots for both absolute values and changes from baseline will be presented over time and by selected subgroups for efficacy (see Section 2.4.1).

Subsections below describe the additional analyses planned for specific continuous endpoints.

5.5.2.2.1. HDV RNA

5.5.2.2.1.1. Change from Baseline to Nadirs

The following change from baseline value to nadir values (defined in Section 5.5) in HDV RNA will be summarized descriptively and displayed graphically via box plots by intervention arm.

- Change from baseline to JNJ-3989 on-treatment nadir
- Change from baseline to overall nadir.

5.5.2.2.1.2. Change from Baseline Over Time

Change from baseline based on \log_{10} transformed values for quantitative HDV RNA to leverage the longitudinal data during the DB study intervention phase will be analyzed using mixed effects model for repeated measures [MMRM] including intervention arm, analysis time point (week), 3 randomization stratification factors (presence of compensated cirrhosis at screening [yes or no], HDV RNA testing laboratory location (China versus outside China), and HBeAg status at screening [positive vs negative]) as fixed effects and baseline HDV RNA (continuous) as covariate. In addition, the above model will be augmented with an intervention arm-by-analysis week interaction term (i.e. treatment-by-time interaction term) to evaluate the change of treatment effect over time. The covariance structure will include a random intercept at the level of the participant to capture between-participant variability, while within-participant variability will be captured with an unstructured (type=UN) covariance matrix. In case of convergence problems, simpler variance-covariance structures such as Toeplitz or AR (1) will be considered. The selection of any of these structures will be determined after exploration of the observed correlation structure. The LS mean of change from baseline, standard error (SE), 95% CI and p-values will be provided.

